12.1 Statistical Methods and Determination of Sample Size

12.2 Data Management

Collection: All data will be collected using the Research Electronic Data Capture (REDCap) tool.²⁰ The sites will use hard copy source documents to collect all physical measurements, assessment data, and subjects will complete self-reports questionnaires only if REDCap is not available or patient prefer hard copy. Study staff will keep all hard copies on site and in designated area with subject specific ID numbers.

Storage: Source document forms will be stored in a secure area at each study site. This will be accessible to study staff only and will be assigned a study ID number. At the end of the study the documents will continued to be stored on site or moved to a separate storage facility and held for the required duration.

Data Entry: Data will be added directly into REDCap when collected. If hard copies are used data will be double entered from the source documents into REDCap as soon as REDCap is available. The data will be reviewed for errors and data will be cleaned prior to analysis. All staff at site will be trained by the sponsor, or designee, or study PI on data collection procedures and protocol implementation.

12.3 Statistical Analysis Plan

Minimization of Bias: Stratified randomization to the study groups within each study site will be conducted. Given that this is a wait list/control design, blinding is not possible. Each subject will be assigned a study ID number that will be used for identification purposes in the data. The study statistician who will have no contact with any study participants and will conduct all analyses.

Missing Data: Randomly missing item responses within the study survey measures will be handled as specified by the measure developers. Nonrandom missing visit data are informative for this study (i.e., may speak to feasibility) – no imputation will be conducted.

Interim Analysis: Given that this is a feasibility study, no interim analyses will be conducted. The primary reason for early stoppage would be adverse events.

Aims:

Primary Aim: To determine the feasibility of use of the Flexitouch® Head and Neck Garment, specifically a) to evaluate implementation fidelity (adherence) and barriers to implementation fidelity, b) to establish safety, and c) to assess satisfaction.

Secondary Aim: To determine the preliminary efficacy of Flexitouch® Head and Neck Garment compared to a wait-list control for the following outcomes: a) reduction in swelling/inflammation, b) function (range of motion cervical, jaw, and shoulder), c) symptoms, and d) quality of life.

12.4 Statistical Analyses:

Aim 1 (feasibility): Descriptive statistics (percentages) will be used to summarize adherence to the protocol, barriers, adverse effects, and ratings of satisfaction. Comparison of the rates observed within each of the study groups will be compared using likelihood Chi-Square tests however it is expected that $\geq 75\%$ of the total number of participants enrolled in the study as a whole will complete the study. At the end of the study, it is expected that participants in the investigational group will report acceptable levels of satisfaction with the device, as indicated by 80% rating the satisfaction items above neutral.

Aim 2 (preliminary efficacy): Descriptive and graphical summaries of the measures at each time of assessment will summarize the overall and group changes in each of the outcome measures over the 8-week study period for each of the groups. Mixed effects general linear models will be used to generate estimates of the interactive effect of the Flexitouch® Head and Neck Garment and time in the study on the primary outcomes. Such an interaction effect would be indicate, for example, larger reduction in symptoms for the intervention group than that observed in the wait list control over the same time period. Bias-corrected effect sizes of garment use on the respective changes will be generated from each of the outcomes. While this study is a preliminary study of efficacy and effect sizes, a maximum alpha level of .05 will be used for statements of “statistical” significance.

Safety Analysis: During the time any participant is using the device, safety checks (Adverse Evetns-CTCAEV4.0, B/P, Pulse, and staging) will be made at defined intervals as noted in section 7.3.

Determination of Sample Size: The primary rationale for study size is the proposed funded time of this study and the number of potential subjects that could be recruited during that time. This is not a hypothesis testing study rather it is a preliminary feasibility and efficacy study for generating observed effect sizes. Nevertheless, samples of 20 individuals in each group (total=40) who successfully complete the 8-week protocol will provide 80% statistical power to detect a differential level of change of approximately 0.9SD (effect size). In other words, assuming a baseline Neck Disability Index (NDI) of 20 (SD=10) and that the wait-list control group demonstrates no change from baseline, a reduction in mean NDI to 11 in the garment group would indicate a statistically significant difference (2-sided alpha-0.05). We have no evidence to hypothesize differences of that magnitude however; we do believe that our sample size will provide sufficient data for estimating reasonable effect estimates for future studies.

13.0 Compensation:

Subjects may be compensated for time and travel at an amount determined by each site.

14.0 Publication Plan:

All information obtained during the conduct of the study will be considered to be confidential and is property of Tactile Medical™. Written permission from Tactile Medical™ is required before disclosing any information relative to this study. All publications (e.g. manuscripts, abstracts, and slide presentations) based on this study must be submitted to Tactile Medical™ for corporate review and approval before submission or according to the individual site clinical trial agreement.

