5.3 Subject Selection

The study sample will be drawn from patients who have received head and neck cancer therapy and have developed HNL secondary to their cancer treatment.

Patients will be recruited from the head and neck cancer clinic at Vanderbilt University and similar clinics at the other investigational sites(s). The patient must have undergone (or attempted and failed) complete decongestive therapy (CDT), or is unable to access CDT as outlined in the inclusion criteria. Only patients who meet the criteria listed below will be considered for the study. A total sample of 40 subjects (20 per group balanced within each site) will be enrolled and those withdrawn for lack of adherence will be replaced, thus we may enroll up to 50 individuals.

5.3.1 Inclusion Criteria :

- Age \geq 18 years
- A previous diagnosis of histologically defined head and neck cancer
- A diagnosis of head and neck lymphedema
- Must be able and willing to participate in all aspects of the study and provide informed consent prior to study participation
- Complete cancer treatment with no evidence of active cancer; all post-surgical swelling must be resolved.
- The head and neck garments must fit appropriately. For patients with a tracheostomy, the fit will be assessed to ensure that the garments do not interfere with their tracheostomy.
- The subject must have experienced at least one of the following:
 - Completion of phase 1 lymphedema care in the past 8 weeks
 - The inability to participate/complete phase 1 care due to:
 - lack of available therapist/clinic
 - lack of insurance coverage or funding to support cost of care.

5.3.2 Exclusion Criteria: Subjects will be determined to be ineligible for this study if they meet any of the criteria described below :

- Uncontrolled hyperthyroidism or parathyroidism (for which endocrinologist recommends against neck compression)
- Carotid sinus hypersensitivity syndrome
- Symptomatic carotid artery disease, as manifested by a recent transient ischemic attack (within 30 days), ischemic stroke, or amaurosis fugax (monocular visual ischemic symptoms or blindness)
- Symptomatic bradycardia in the absence of a pacemaker
- Internal jugular venous thrombosis, acute or within 3 months
- Increased intracranial pressure or other contraindications to internal or external jugular venous compression
- Acute radiation dermatitis, unhealed surgical scar, unhealed or open wound(s), surgical flap less than 6-8 week post-operative

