7.2.2 Laboratory Testing

Women of childbearing potential, defined as premenopausal, intact ovaries and uterus, and not on birth control, will be tested for pregnancy using a self-administrator urine pregnancy test. If the pregnancy test is positive, the subject will be excluded from the study.

7.2.3 Feasibility (Appendix E):

7.2.3.1 Adherence and barriers (Both Groups): Subjects will keep a diary of device use and list barriers to use of device (investigational group). A self-care checklist will be completed each week they are in the study (both groups).

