7.2.3.2 Safety (Both Groups) will be evaluated using CTCAE V4.0¹¹

7.2.3.3 Pre and Post treatment Survey (Intervention Group Only): Subjects will complete a pre and post treatment survey. The survey will be administered at the baseline visit and at the end of the intervention.

7.2.4 Swelling/Inflammation (Appendix F):

7.2.4.1 Endoscopy with Modified Patterson Scale: The Patterson Scale evaluates internal edema in the pharynx and larynx. The Modified Patterson Scale, with established face validity, includes anatomical sites that may develop internal edema.¹²

7.2.4.2 Cytokines: The study nurse or phlebotomist will draw blood at baseline and at the 8-week visit. The following inflammatory markers will be assessed: IFN γ TNF- α , TGF- β , IL-1b, and IL-6. MMP-2, MMP-9, and CRP will also be assessed if testing is available.

7.2.4.3 Digital Photography: At the visits outlined in the Study Schedule of Activities table in section 7.4, subjects will have photos taken of their affected areas to evaluate external swelling/inflammation. These photos will be taken according to the standard procedure as outlined in Appendix F.

7.2.4.4 Grading of External Lymphedema: Trained study personnel will complete a physical examination of the head and neck area. Grading will be documented via the Head and Neck Lymphedema and Fibrosis Assessment criteria.¹³

7.2.5 Function (Appendix G):

7.2.5.1 Neck Disability Index (NDI): This 10-item instrument assesses components of daily life that may be affected by neck pain and dysfunction. Items include pain, personal care, lifting, reaching, headache, concentration, work, driving, sleeping, and recreation. Internal consistency of the 10-item scale is adequate ($\alpha = .89 - .92$).^{14,15} Factor analysis identified one dimension. Stability of the instrument also is adequate ($r = .89$). Validity of the NDI was supported by the moderate to strong correlations with self-reported activity improvement following treatment and pain.

7.2.5.2 Voice Handicap Index (VHI): This 30 item instrument taps function, emotion, and physical areas that may be affected by

voice disorders such as those caused by chemo-radiation therapy for HNC.¹⁶ Internal consistency of the 30-item scale is adequate ($r=0.95$).

7.2.5.3 Cervical and Shoulder ROM: These measurements will be taken according to the instructions provided in Appendix G. The measurements will be taken at intervals outlined in the Study Schedule of Activities table (section 7.4).

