Self-care Checklist			weekly		
Safety					
Adverse Events- CTCAEV4.0*			√	√	√
Satisfaction					
Pretreatment survey**		√			
Post treatment survey **					√
Swelling/Inflammation					
Internal- Endoscopy/Patterson Scale		√			√
Digital Photography		√	√	√	√
Grading and Staging*	√	√	√	√	√
Cytokines		√			√
Function					
Range of motion-jaw, shoulder, neck		√		√	√
Patient Reported Outcome- Neck Disability Index		√		√	√
Patient Reported Outcome- Voice Handicap Index		√		√	√
Symptoms					
Vanderbilt H and N Symptom Survey		√		√	√
Lymphedema Symptom Intensity and Distress Scale		√		√	√
Quality of Life					
Linear Analog Self- Assessment		√		√	√

*=safety checks at week 9, 12, &16 for wait-list group opting to use the device

**=intervention group only

8.0 Study Device Accountability (Appendix I):

The site must maintain a device accountability log for the Flexitouch®. Completion of this log will ensure that all study devices are properly tracked and accounted for throughout the study from the time they are received by the institution to the time they are returned to the study sponsor or other designated site. Device location, subject ID assigned, date subject returned to site, controller disinfected, and final disposition (e.g., returned to sponsor, garments discarded) of all Flexitouch® controllers, and garments will be documented.

Tactile Medical™ must also maintain device accountability documenting all shipments and returns of study devices by serial number, date, and person completing the log. Storage locations for the study devices and garments will be secure (i.e., locked and away from other devices) with access restricted only to investigators and authorized research personnel. At the conclusion of the treatment period, the subject will return the Flexitouch® controller to the study site. Garments may be retained by the subject or discarded. Site personnel will return all controllers and any unused garments to Tactile Medical™ at the completion of the study.

9.1 Risk Analysis and Adverse Events:

9.2 Risk Analysis: The subjects enrolled in the study are not expected to be at any higher or additional risk than those who undergo in-clinic CDT. There is minimal risk with CDT. These risks may include but are not limited to increased swelling and pain.

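### Aim 1 compares rates between arms of 20 with a large-sample likelihood-ratio chi-square test, whose true type I error reaches 8.5% when the common rate is near 10%

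*Combined protocol and SAP*

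**What the plan says.** Section 12.4, Aim 1, begins descriptively: "Descriptive statistics (percentages) will be used to summarize adherence to the protocol, barriers, adverse effects, and ratings of satisfaction". It then adds a between-arm test: "Comparison of the rates observed within each of the study groups will be compared using likelihood Chi-Square tests". No exact test, sparse-cell rule or continuity correction appears there or elsewhere, and the sentence does not list the rates to be compared.

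Arm sizes are in Section 5.3: "A total sample of 40 subjects (20 per group balanced within each site) will be enrolled", with replacements allowing up to 50 in total. Safety is part of the primary aim, and Section 7.2.3.2 covers both arms: "Safety (Both Groups) will be evaluated using CTCAE". The weekly self-care checklist (Section 7.2.3.1) is also kept by both arms, and completion can be counted in both. The diary entries for adherence and barriers and the pre- and post-treatment surveys are marked "intervention group only" in the Section 7.4 schedule.

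The only significance level for the analyses is in the Aim 2 paragraph: "a maximum alpha level of .05 will be used for statements of" statistical significance. The sample-size paragraph adds: "This is not a hypothesis testing study rather it is a preliminary feasibility and efficacy study for generating observed effect sizes".

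**The concern.** The likelihood-ratio statistic is referred to a chi-square distribution that is accurate in large samples. With 20 per arm and an uncommon event, expected event counts are one or two per arm, and the statistic is too large when one arm has no events. Adverse-event categories are where such tables are most likely. A pilot with safety in its primary aim could then report a significant difference on three events against none. That could be a false signal of harm or, if the events fall in the wait-list arm, a false signal of benefit.

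**Working it through.** **Inputs.** 20 per arm (Section 5.3), 1:1 allocation (Section 6.3), and the likelihood-ratio chi-square on 1 degree of freedom (Section 12.4, reading "likelihood" in that sense). Level 0.05 is assumed to carry over from Aim 2. The common event rate is not given for adverse events, so it is varied.

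**The plan's own figure.** The documents give no type I error for Aim 1. Their one power figure (80% for 0.9 SD with 20 per arm) reproduces: 79.2% by the noncentral t, 81.2% by the normal approximation. It concerns Aim 2 and does not bear on this test.

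**One sparse table, 3/20 v 0/20.** Expected counts are 1.5 events and 18.5 non-events per arm.

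- Likelihood ratio: G² = 2 Σ O ln(O/E) = 2[3 ln(3/1.5) + 17 ln(17/18.5) + 20 ln(20/18.5)] = 4.40, p = 0.036.
- Pearson: X² = Σ (O − E)²/E = 2(1.5²/1.5) + 2(1.5²/18.5) = 3.24, p = 0.072.
- Barnard (score-based) 0.086; Boschloo 0.154; Fisher 0.231.
- Risk difference 15 points, Miettinen-Nurminen 95% CI −3 to 36.

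For 4/20 v 0/20 the p-values are 0.014 (likelihood ratio), 0.035 (Pearson), 0.039 (Barnard), 0.061 (Boschloo) and 0.106 (Fisher).

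**True type I error.** For a common rate π, sum the product of two Binomial(20, π) probabilities over all 21 × 21 outcomes with G² ≥ 3.841:

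| Common rate | Likelihood-ratio type I error |
|---|---|
| 3% | 2.3% |
| 5% | 5.4% |
| 8% | 8.3% |
| 10% | 8.5% |
| 15% | 6.8% |
| 20% | 5.5% |
| 25% (or 75%) | 5.2% |
| 50% | 4.3% |

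The maximum is 8.53%, at a rate of about 9.4%. The error exceeds 5% for rates from 4.7% to 38%, and 6% from 5.4% to 17.5%; the mirror-image rates behave identically.

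**Source of the excess.** At π = 10% the chance of 3 v 0 in either direction is 2 × [1140 × 0.1³ × 0.9¹⁷] × 0.9²⁰ = 2 × 0.190 × 0.122 = 0.046. That result alone supplies 4.6 of the 8.5 points.

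**Other arm sizes.** The peak is 8.75% at 25 v 25, 9.4% at 21 v 19, 6.3% at 22 v 18 and 6.5% at 25 v 20.

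**Alternatives at 20 per arm.**

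| Test | Maximum type I error | Power at 25% v 5% |
|---|---|---|
| Likelihood ratio | 8.53% | 49% |
| Pearson | 5.34% | 44% |
| Barnard | 4.98% | 44% |
| Boschloo | 4.64% | 38% |
| Fisher | 2.53% | 30% |

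Pearson's maximum rises to 6.5% at 25 per arm.

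**The case against.** The 8.5% figure is close to the worst case, at a rate the documents never state. The one rate they anticipate for something measured in both arms is completion of at least 75%, and there the test is near nominal. Aim 1 is mainly descriptive, its two benchmarks (75% completion overall, 80% satisfaction in the device arm) are not between-arm comparisons, and the plan disclaims hypothesis testing. All of this stands, and it limits the weight of the point.

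For safety, a liberal test flags too much rather than too little, and a stricter test loses sensitivity. This stands in part. The loss is real but small with Barnard's test, and the error can equally produce a spurious benefit.

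The figures also depend on the final arm sizes. If replacements accumulate in the device arm, 3/25 there against 0/20 gives p=0.054. But 0/25 against 3/20 gives p=0.023, and a 21 v 19 split raises the peak to 9.4%. Final arm sizes cannot be known in advance, which favours a test that holds its level at any of them. For the same reason, switching to Pearson would nearly suffice at 20 v 20 but is not guaranteed.

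Calling the study non-hypothesis-testing does not remove the problem, since a test is still named. If the comparison is meant to be descriptive, an estimate with an interval is the natural replacement.

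**Conclusion.** The concern holds. With 20 per arm, the named test has a true type I error of up to 8.5% against a nominal 5%, and above 6% for common rates of 5.4% to 17.5% or their mirror image. It is conservative below 4.7% and close to nominal at 75% completion. The conclusion rests on reading the test as the likelihood-ratio chi-square with its large-sample reference, on equal arms, on the .05 level applying to Aim 1, and on some adverse-event rates falling in the affected range. The documents neither confirm nor exclude the last two. The practical effect is modest and confined to sparse tables, where it can change the reported result. No feasibility benchmark is affected.

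**What to change.** In Section 12.4, name the rates compared between arms (adverse events, completion, self-care checklist items). For each, report the risk difference with a Miettinen-Nurminen 95% confidence interval as the main result. If a p-value is wanted, specify one unconditional exact test in advance, either Barnard's score-based test or the stricter Boschloo test, and state the level that applies to Aim 1.

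As an optional clarification, say that the comparison excludes items recorded only in the device arm, and give those as percentages with Clopper-Pearson intervals. For example, 16/20 against the 80% satisfaction target gives 56% to 94%.

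The cost is SAP wording and some power. At a true 25% v 5%, the loss from 49% is about 5 points with Barnard and 11 with Boschloo. Fisher's test would lose 19 and is the costliest choice for a safety comparison.

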- Facial or head and neck dermal metastasis
- Acute facial infection (e.g., facial or parotid gland abscess)
- Any condition in which increased venous and lymphatic return is undesirable
- History of pulmonary edema or decompensated congestive heart failure with in six (6) week of enrollment.
- Subject is pregnant or trying to become pregnant

5.3.3 Subject Withdrawal or Early Termination:

Subjects will exit the study if they meet any of the following criteria:

- Subject death
- Subject voluntarily withdraws
- Subject experiences a serious adverse event that in the investigator's clinical judgment necessitates study discontinuation
- Subject acquires any of the exclusion criteria, except
 - In the case of a subject acquiring an infection, they may remain in the study per the discretion of the investigator. Detailed information regarding the infection, nature, treatment, and duration, will be recorded.
- Non-adherence with any study procedures as defined by no use of device during a consecutive 7-day period as documented on the diary or failure to complete required documents.

5.4 Dosage:

Wait-list Control Group: Subjects will continue their home care regimen as defined by their physician/healthcare provider. The home care regimen may include:

- self-MLD
- exercise
- skin care
- wearing an appropriate compression garment.

After 8 weeks, the subject will then receive treatment as outlined below in the investigational group if they so desire.

Investigational Group: Subjects in the investigational group will use the Flexitouch® pneumatic compression device in addition to the home care regimen defined by their treating physician/healthcare provider. The subject will complete two treatment sessions daily using the Flexitouch® head and neck system for the full 8 weeks of study participation. The twice daily treatment will include the H1 program for the head, neck and chest with an approximate 25-43 minute single cycle time as outlined in the Flexitouch® System User Guide (Appendix A). Instructions for the application of the head and neck garments are located in Chapter 6 of the Flexitouch® System User Guide (Appendix A). The home care regimen may include:

- self-MLD
- exercise
- skin care
- wearing an appropriate compression garment, if applicable

5.5 Study Timetable:

	1- 3months	4-6 months	7-9 months	10-14 months
IRB Review	X			
Enrollment	X	X	X	
Treatment		X	X	
Data Entry		X	X	
Data Analysis			X	
Manuscript Draft			X	
Publication				X

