Subjects randomized to the investigational group at each site will follow the Study Schedule of Activities table in section 7.4 and will complete the study in 8 weeks. The subjects that are randomized to the waitlist group at each site will complete all study activities as outlined below in table 7.4. After completing the 8 weeks of the standard regimen, the subjects may choose to receive the same treatment as was implemented in the investigational group. No study data will be completed; however, patients opting to use the device will be seen at weeks 9, 12, and 16 for a documented safety check as outlined in section 7.4.

Research team members will provide the subjects with a self-care kit and provide instructions on how to use the kit. All subjects will leave the initial baseline visit with the self-care kit (Appendices D & E) that includes:

- Subject Diary (intervention group only)
- Self-care checklist
- Dates and Times for their upcoming appointments
- Contact information and instructions to call if any questions

6.4 Follow Up Visit(s):

The subject follow up visits will occur at 1 and 4 weeks (± 3 days). The study staff will collect the checklist and review the subject diary with the intervention patients during each visit to ensure that all entries are complete and understood by the study staff. Any corrections must be made by the subject, and initialed and dated by them. At the visit, the subject will undergo the study procedures as outlined in the Study Schedule of Activities in section 7.4.

6.5 Final Visit:

The final study visit will occur at 8 weeks (± 3 days). At this visit, the subject will undergo the study procedures as outlined in the Study Schedule of Activities in section 7.4. The study staff will collect the checklist and review the subject diary with the subject during each visit to ensure that all entries are complete and understood by the study staff. Any corrections must be made by the subject, and initialed and dated by them.

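### The device-non-use exit can operate only in the device arm, so that arm can be observed for harms for less time, and the crude adverse-effect percentages in section 12.4 make no allowance for it

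*Combined protocol and SAP*

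**What the plan says.** Establishing safety is part (b) of the primary aim (section 4.3). Adverse events are graded by CTCAE in both groups (7.2.3.2), with review at weeks 1, 4 and 8 (7.4).

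Section 5.3.3 opens its list with "Subjects will exit the study if they meet any of the following criteria". One criterion is "Non-adherence with any study procedures as defined by no use of device during a consecutive 7-day period as documented on the diary", which continues "or failure to complete required documents". The kit list in section 6.3 has "Subject Diary (intervention group only", and the table in 7.4 marks the diary rows the same way. Section 5.4 describes the comparator: "Wait-list Control Group: Subjects will continue their home care regimen as defined by their physician/healthcare provider". It adds: "After 8 weeks, the subject will then receive treatment as outlined below in the investigational group if they so desire".

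Section 5.3 expects some of these withdrawals: "those withdrawn for lack of adherence will be replaced, thus we may enroll up to 50 individuals".

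For the analysis, section 12.4 (Aim 1) gives percentages for adverse effects alongside adherence, barriers and satisfaction, and then states: "Comparison of the rates observed within each of the study groups will be compared using likelihood Chi-Square tests". Section 12.3 rules out imputing missing visits. Neither section gives a person-time or time-to-event summary, or a denominator rule for subjects who exit or are replaced.

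**The concern.** The device-non-use part of the exit criterion needs a device and a diary. In weeks 0-8 only the device arm has either, so this route out of the study is closed to the wait-list arm. The missing-documents part can apply in both arms. Exit ends observation as far as the documents show: sections 6.2 to 6.5 describe no early-termination visit or later safety contact, and the safety paragraph in 12.4 ties the checks to the time a participant is using the device.

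A crude percentage over all randomised subjects gives a subject observed for 4 weeks the same weight as one observed for 8, and in effect counts the unseen weeks as event-free. The likelihood chi-square is a valid comparison of two proportions. To read its result as a comparison of harm risk, however, the two arms need similar observation time. Where only the device arm loses time, the error favours the device.

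**Working it through.** **The plan's own figure.** The only power statement is 20 completers per group, 80% power, 0.9 SD, two-sided alpha 0.05. The normal approximation gives n = 2 × (1.96 + 0.84)² / 0.9² ≈ 19.4, so 20 per group. Power at 20 is 81.2% by that approximation and 79.2% by the noncentral t. The figure reproduces, but it concerns change scores. No figure is given for adverse events.

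**When an exit can be found.** Non-use counts as documented on the diary, and staff review the diary at the week 1, 4 and 8 visits (6.4, 6.5), which are also the harm-review visits. On the documented route, exit therefore falls at about week 1 or week 4. Non-use found at week 8 costs no observation.

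**Inputs.**
- From the documents: 8 weeks of follow-up, 1:1 allocation, at most 50 enrolled, at most 10 replacements.
- Assumed: 25 per arm, wait-list arm fully observed, equal constant hazard in both arms, exit unrelated to harm, no harm data after exit, all randomised subjects in the denominator, true 8-week rate p of 10%, 20% or 40%, and 5 or 10 device-arm exits.

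**Observation time.** Mean device-arm weeks = [(25 − k) × 8 + k × w] / 25, for k exits at week w.
- 5 exits at week 4: (160 + 20) / 25 = 7.2 weeks, 90% of planned.
- 10 exits at week 4: (120 + 40) / 25 = 6.4 weeks, 80%.
- 5 exits at week 1: (160 + 5) / 25 = 6.6 weeks, 82.5%.
- 10 exits at week 1: (120 + 10) / 25 = 5.2 weeks, 65%.

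**Spurious gap.** With f = k/25, the expected device-arm percentage is (1 − f)p + f[1 − (1 − p)^(w/8)]. It falls short of p by f[(1 − p)^(w/8) − (1 − p)]. For p = 0.40, f = 0.2, w = 4: 0.2 × (0.7746 − 0.60) = 0.035.

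| Exits | p = 10% | p = 20% | p = 40% |
|---|---|---|---|
| 5 at week 4 | 1.0 points | 1.9 | 3.5 |
| 10 at week 4 | 1.9 | 3.8 | 7.0 |
| 5 at week 1 | 1.7 | 3.4 | 6.8 |
| 10 at week 1 | 3.5 | 6.9 | 13.5 |

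**Against sampling error.** The standard error of the difference, √(2p(1 − p)/25), is 8.5, 11.3 and 13.9 points at p = 10%, 20% and 40%.

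**Effect on detecting harm.** If the device truly doubled the hazard and the wait-list rate were 40%, exact enumeration of the likelihood chi-square at 25 per arm gives 44.7% power to show excess harm with no exits. This falls to 31.5% with 5 exits at week 4 and 20.4% with 10.

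**What person-time does.** Under the same assumptions with p = 40%, the first-event rate per week at risk is −ln(0.6)/8 = 0.064 in both arms, however many subjects exit and whenever they do. The spurious gap disappears.

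**The case against.** The strongest reply is that this is a pilot which disclaims hypothesis testing, that no safety decision hangs on the test, and that the gaps in the more plausible scenarios are small against sampling error. The gaps are indeed small: at rates of 10-20% with week-4 exits they are 1-4 points. But establishing safety is a primary aim, and the distortion sits in the reported percentage whether or not significance is claimed.

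A second reply is that the chi-square sentence does not name adverse effects and runs straight on to study completion. That is true. However, diary adherence, device barriers and the satisfaction surveys are collected in the device arm only, so adverse effects are among the few listed rates that can be compared between arms.

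A third is that a completers-only analysis would equalise observation time. It would, by dropping the exited device users and their harms altogether, which is no remedy.

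Four stronger readings may tempt a reader, and the documents do not support them:
- That the device arm will be observed for less time. This happens only if exits occur and wait-list withdrawals, including those for missing documents, do not offset them.
- That a subject who stops in week 2 leaves in week 3 and misses the week-4 harm review. On the described route, the stop would normally be found at the week-4 visit, where harms are reviewed.
- That the bias must grow if pain or swelling causes the non-use. The event may already be recorded before exit, so the bias may differ in either direction.
- That ten device-arm exits are to be expected. Ten is the overall cap. The synopsis applies it to early withdrawals generally, and lack of adherence can also arise in the wait-list arm. Ten of 25 would also leave 15 device completers, short of the 20 wanted.

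**Conclusion.** The point holds as a possible bias built into the design and not addressed in the analysis. One exit route is open to the device arm alone in weeks 0-8, observation is not described beyond exit, and 12.4 compares crude percentages. If such exits occur without matching wait-list losses, the device arm tends to look safer.

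The size cannot be known from the documents. With 5 exits at week 4 it is about 1.0 to 3.5 points over true rates of 10% to 40%. With 10 it is about 1.9 to 7.0 points, as an extreme case. Week-1 exits roughly double these figures, but require a full first week without recorded device use. All of this rests on equal constant hazards, 25 per arm, a fully observed wait-list arm and exit unrelated to harm. This is a cheap improvement worth making, not a flaw that invalidates the trial.

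**What to change.** In section 12.4, for adverse effects only:

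- Include every randomised subject, also those who exited and were replaced.
- Restrict the between-arm comparison to weeks 0-8, so that the week 9, 12 and 16 checks on wait-list subjects who take up the device do not enter it.
- Beside each percentage, state the person-weeks from randomisation to last safety contact, by arm.
- Base the comparison on events per person-week, as a rate difference or ratio with a 95% interval, and say whether repeat events in one subject count.
- Give the Kaplan-Meier proportion with a first event by week 8 as support, noting that it assumes exit is unrelated to harm.

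The chi-square can stay for the other rates. Confirm that exit and last-contact dates are captured, since the documents do not list such fields.

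The cost is a few lines of text and a slightly longer table, with no new visits or subjects. Some onset dates will be known only to the interval between visits, and the device-arm figure may be less favourable. The exit rule is not changed.
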